#### 5.1 Standard Care

Patients arriving to the control EDs (all study phases) and the intervention ED during study Phase #1 will receive care as per then-current ED practices and protocols, guided by clinician judgment within a system-wide care process model for sepsis. As of early 2019, ED standard care for sepsis applicable at all study sites includes a standardized Care Process Model, expected completion of a standardized checklist, and standardized order sets.

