#### 5.2 Code Sepsis Protocol

The Code Sepsis protocol (Figure 3) has six steps developed in collaboration with ED-based study team members and ED leaders (including physicians, nurses, pharmacists, and others) from the implementation ED and the Intermountain system. The current draft protocol was further iteratively revised based on input derived from the proposed multidisciplinary team during *in situ* high-fidelity simulation and during informal/ad hoc operationally-oriented pilot testing of steps 1-5 during live patient care. The below protocol will be adapted further prior to and after implementation to ensure the protocol is feasible, efficient, and functions as intended based on stakeholder input and, as needed, additional protocol element testing during simulation and/or live patient care. Further revision will occur, during the protocol run-in phase and as needed based on observed findings and stakeholder input.

Figure 3. Current Code Sepsis protocol based on iterative revision using simulation testing, stakeholder input, & live pilot testing.

- Identify likely sepsis patient from prehospital notification call data (nurse), at ED triage (nurse/physician), or on ED room placement (nurse or physician), adapting local and national practice for stroke team activation.
- 2) Mobilize ED personnel and equipment to meet patients on arrival to the ED room using methods and communication networks already developed for ED trauma and stroke teams.
- 3) Concurrent patient evaluation and data collection by multiple disciplines (20-25 minutes), to include bedside assessment (e.g. history, examination, vital signs, allergy and medication history) by the physician, nurse and pharmacist; IV placement; blood and urine sampling; point-of-care laboratory testing, including lactate and urinalysis; and portable X-ray imaging. Appropriate therapeutic interventions will continue in parallel during the nominal data collection phase.
- 4) Team "huddles" to decide if sepsis diagnosis has been confirmed, disproven, or remains indeterminate. The physician may complete this step by announcing clinical decision-making to the team at any time. The nurse will request a decision huddle at 25 minutes into the Code Sepsis event if it has not previously been performed.

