#### 7.3 Sample size/power analysis

Using 2013 to 2017 data from our study hospitals, we estimated conservatively that the intervention ED provides care for 1,650 sepsis patients annually (approximately 4.5 sepsis patients per day) and the

control EDs together care for a total of 2,200 sepsis patients annually (approximately 6 sepsis patients per day). Based on the design and our pilot testing of the Code Sepsis protocol, a very conservative estimate of door-to-antibiotic time for patients who receive antibiotics after evaluation under the Code Sepsis protocol is 50 minutes. By comparison, our preliminary data from 2013 to 2017 indicates current mean (SD) door-to-antibiotic time for ED sepsis patients is 170 (±75) minutes and that only 5% of patients currently receive antibiotics within 1 hour of ED arrival. Assuming (again conservatively) that the Code Sepsis protocol is activated for 30% of sepsis patients treated in the intervention ED during the full implementation phase (study phase #3), we will have 90% power to detect a difference-in-differences change of 16 minutes or more in door-to-antibiotic time associated with Code Sepsis implementation, with the measurement population being all ED sepsis patients. Power calculations employed Monte Carlo simulations, for which technical details are available upon request.

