limited in that it only considers the control and treated groups during the pre-implementation phase. If the pre-test of parallel trends assumption fails, then we will weight the gamma regression model with propensity scores. As demonstrated by Stuart *et. al*, this will balance the covariates amongst the four study groups defined by their treatment status as well as time (pre vs post). We will leverage the covariate balancing propensity score (CBPS) library in R to generate propensity scores. This weighting approach can recover treatment effects in that it allows for adjustments due to observed baseline covariates that differ either across groups or over time. Covariates that will be used in generating propensity scores will include age; sex; weighted Elixhauser comorbidity score; English language preference; first-available heart rate, temperature, systolic blood pressure, and respiratory rate; acute physiology score; ED arrival at nightime (10 pm to 6:59 am), ED arrival on weekend (midnight Saturday to 11:59 pm Sunday), SARS-CoV-2 test result (positive, negative, or not performed during ED-associated hospitalization or within 14 days preceding ED arrival); and insurance type. For analyses involving a cohort of patients with sepsis, propensity score covariates will additionally include arrival to ED via ambulance; presentation from a long term care facility; serum lactic acid level checked and ≥2 mmol/dL; ED SOFA score; and ED-diagnosed infection source.

In order to account for the right skew known to exist in door-to-antibiotic time we will use generalized linear gamma regression to estimate the DID. Evaluation of secondary outcomes will employ an analogous approach using multivariable linear, Poisson, logistic, or gamma regression as appropriate. Data from the wash-in phase will be excluded from DID analyses. All multivariable models will be adjusted for demographic and clinical parameters with known or plausible associations with both outcomes and treatment hospital, presentation before or after Code Sepsis implementation, and/or Code Sepsis activation as well as select precision variables as detailed below. Analyses for secondary, safety, and heterogeneity of treatment effect outcomes will not be adjusted for multiple comparisons and will therefore be considered hypothesis generating.

Statistical significance will be set to p < 0.05. All analyses will be conducted with R.

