#### Primary and secondary analyses

```
dag {
"Arrival to intervention ED post-intervention" [exposure,pos="-1.196,0.491"]
"Door-to-antibiotic time" [outcome,pos="1.007,0.477"]
"ED arrival mode" [adjusted,pos="-0.485,0.630"]
"Elixhauser score" [adjusted,pos="0.565,-0.356"]
"Illness severity" [latent,pos="-0.139,0.781"]
"Initial SBP" [adjusted, pos="-0.104, 1.525"]
"Long-term care" [adjusted,pos="-1.122,-0.086"]
"O2 sat" [pos="1.453,0.736"]
"Preferred language" [adjusted,pos="-0.378,-0.501"]
"SOFA score" [adjusted,pos="0.269,1.938"]
"Suspected infection source" [adjusted,pos="0.536,-1.411"]
APS [adjusted, pos="-0.561, 1.300"]
Age [adjusted, pos="-1.631, -0.018"]
GCS [pos="0.214,0.680"]
HR [pos="1.331,1.495"]
Lactate [pos="0.977,2.039"]
RR [pos="1.106,1.680"]
Sex [adjusted,pos="-1.399,-0.383"]
Temperature [pos="0.798,1.651"]
WBC [pos="1.406,1.039"]
"Arrival to intervention ED post-intervention" -> "Door-to-antibiotic time"
"ED arrival mode" -> "Arrival to intervention ED post-intervention"
"ED arrival mode" -> "Door-to-antibiotic time"
"Elixhauser score" -> "Arrival to intervention ED post-intervention"
"Elixhauser score" -> "Door-to-antibiotic time"
"Elixhauser score" -> "Illness severity"
"Elixhauser score" -> "Long-term care"
"Illness severity" -> "ED arrival mode"
"Illness severity" -> "Initial SBP"
"Illness severity" -> "SOFA score"
"Illness severity" -> APS
"Illness severity" -> GCS
"Initial SBP" -> "Door-to-antibiotic time"
"Initial SBP" -> "SOFA score"
```

```
"Initial SBP" -> APS
"Initial SBP" -> Lactate
"Long-term care" -> "Arrival to intervention ED post-intervention"
"Long-term care" -> "ED arrival mode"
"Long-term care" -> "Suspected infection source"
"O2 sat" -> "Door-to-antibiotic time"
"O2 sat" -> "SOFA score"
"O2 sat" -> APS
"Preferred language" -> "Arrival to intervention ED post-intervention"
"Preferred language" -> "Door-to-antibiotic time"
"Preferred language" -> "ED arrival mode"
"SOFA score" -> "Door-to-antibiotic time"
"Suspected infection source" -> "Door-to-antibiotic time"
"Suspected infection source" -> "Illness severity"
APS -> "Door-to-antibiotic time"
Age -> "Arrival to intervention ED post-intervention"
Age -> "Door-to-antibiotic time"
Age -> "ED arrival mode"
Age -> "Long-term care"
Age -> "Preferred language"
GCS -> "Door-to-antibiotic time"
GCS -> "SOFA score"
GCS -> APS
HR -> "Door-to-antibiotic time"
HR \rightarrow APS
Lactate -> "Door-to-antibiotic time"
RR -> "Door-to-antibiotic time"
RR -> APS

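### As written, the lactate flag in the fallback propensity weights has a cut-off of 20 mmol/L, and with the unit corrected it still depends on a test that Code Sepsis includes for activated patients

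*SAP*

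**What the plan says.** The weights are a conditional fallback in the SAP, Data analysis: "If the pre-test of parallel trends assumption fails, then we will weight the gamma regression model with propensity scores". A core covariate list serves all cohorts, and extra terms are added for sepsis patients: "For analyses involving a cohort of patients with sepsis, propensity score covariates will additionally include arrival to ED via ambulance". One of those extra terms is "serum lactic acid level checked and ≥2 mmol/dL". The SAP justifies the weighting as allowing "adjustments due to observed baseline covariates that differ either across groups or over time".

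No other place in either document gives a lactate cut-off or unit. The flag is a single binary term with no time window for the test. The SARS-CoV-2 term in the same list has a separate level for patients not tested, and a window.

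Lactate is not in the SAP's covariate list for the primary and secondary models. In the SAP appendix, the graph for those analyses draws lactate as a cause of door-to-antibiotic time, does not mark it as adjusted, and has no arrow from the exposure to it.

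In Protocol 5.2, step 3 of Code Sepsis includes "point-of-care laboratory testing, including lactate and urinalysis". The same section adds Code Sepsis diagnostic order sets at the intervention ED. For planning, Protocol 7.3 assumes that "the Code Sepsis protocol is activated for 30% of sepsis patients treated in the intervention ED". Standard care at all sites (Protocol 5.1) already has a care process model, with "expected completion of a standardized checklist, and standardized order sets". Its lactate testing rate is not stated.

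**The concern.** There are two separate faults.

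The first is the unit. A prespecified threshold should be executable as it stands. Taken literally, this one would make the indicator almost constant, so the weights would carry no information on lactate.

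The second remains after the unit is corrected. The flag equals 1 only if lactate was measured, and the intervention can change who is measured in one of the four site-by-period cells. If testing rises there, the flagged share rises even when the patients are no sicker. Weighting that cell back to the share in the other cells under-represents patients with truly high lactate. If such patients tend to be treated sooner, the weighted mean time in that cell is too long, and the difference-in-differences coefficient moves toward no effect.

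The weights would apply to the primary outcome in exactly the situation where the unweighted analysis has lost credibility.

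**Working it through.** The documents give no figure of their own for this covariate, so there is nothing to reproduce.

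**Unit.** 1 L = 10 dL, so 2 mmol/dL × 10 = 20 mmol/L. If 2 mmol/L was meant, the written unit would need 0.2 mmol/dL. The factor is exactly 10.

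**How empty the literal flag would be.** Assumption, not in the documents: lactate is log-normal with median 2 mmol/L and log-SD 0.6 to 0.7.

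- z = ln(20/2)/0.6 = 3.84, upper tail 0.006%
- z = ln(20/2)/0.7 = 3.29, upper tail 0.05%
- Of the 1,650 sepsis patients a year at the intervention ED (Protocol 7.3): about 0.1 to 0.8 patients

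**Testing effect with the unit read as mmol/L.** Inputs:

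- a = 0.30, activated share of sepsis patients (Protocol 7.3)
- all activated patients are tested, and the others keep the baseline rate (assumption)
- q0 = baseline testing rate (not in the documents, shown as a range)
- p = 0.50 truly at or above the cut-off in every cell (assumption)
- high-lactate patients are treated 15 to 45 minutes sooner (assumption)
- the other three cells stay at q0, and the weights bring the intervention post cell to their flagged share (assumption)

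Formulas:

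- Testing after implementation: q1 = a + (1 − a) × q0
- Flagged share: p × q0 before, p × q1 after
- Truly high among unflagged patients after: p(1 − q1)/(1 − p × q1)
- Weighted share truly high after: p × q0 + (1 − p × q0) × p(1 − q1)/(1 − p × q1)
- Gap = p minus that share, which simplifies to p(1 − p)(q1 − q0)/(1 − p × q1)

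For q0 = 70%: q1 = 0.30 + 0.70 × 0.70 = 0.79. The flag goes from 0.350 to 0.395. Gap = 0.25 × 0.09/0.605 = 0.037. Multiplying by 15 to 45 minutes gives 0.6 to 1.7 minutes.

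| Baseline testing q0 | After q1 | Flag before | Flag after | Truly high after weighting | Gap (points) | Bias toward no effect (min) |
|---|---|---|---|---|---|---|
| 50% | 65% | 25.0% | 32.5% | 44.4% | 5.6 | 0.8 to 2.5 |
| 70% | 79% | 35.0% | 39.5% | 46.3% | 3.7 | 0.6 to 1.7 |
| 90% | 93% | 45.0% | 46.5% | 48.6% | 1.4 | 0.2 to 0.6 |
| 100% | 100% | 50.0% | 50.0% | 50.0% | 0 | 0 |

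Testing below 50% would give somewhat more. At 30%, q1 = 0.51 and the gap is 0.25 × 0.21/0.745 = 7.0 points, or 1.1 to 3.2 minutes.

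**The case against.** The unit is most likely a typing slip, and nothing shows that it reached the dataset or the code. That stands, and it is why the unit should be confirmed against the dataset. That 2 mmol/L was intended is likely, but it is an inference.

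A reader might infer that Code Sepsis makes lactate testing universal at the intervention ED. The documents do not say that. The test is listed for activated patients, and Protocol 8.3.4 expects many sepsis patients not to trigger an activation. The new order sets could raise testing in others too. On the other hand, activated patients may already have been tested more often than average under standard care, whose checklist and order sets could imply a high baseline rate.

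A reader might also picture testing rising from 70% to 95%. With the same formula that gives 0.25 × 0.25/0.525 = 11.9 points, or 1.8 to 5.4 minutes. If only activated patients gain testing, it needs (0.95 − 0.70)/0.30 = 83% activation, against 30% planned.

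It would also be too strong to say that the flag either balances nothing or balances only testing. In mmol/L it carries severity as well as testing. Even read literally, the other covariates are still balanced. The weights include SOFA, acute physiology score and first vital signs, and the SAP's regression covariates include SOFA, acute physiology score, systolic pressure and temperature. These should absorb part of the gap, which the arithmetic above ignores.

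Finally, the SAP's own graph has lactate as a cause of the outcome, so removing it has a price, and its absence from the main covariate list is only weak support for removal. The interrupted time series sensitivity analysis also addresses non-parallel trends and specifies no propensity weights. These arguments limit the size and reach of the problem. They do not correct the unit, and they do not make the flag a baseline variable.

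**Conclusion.** The point holds in limited form. The unit error is exact: the written cut-off is 20 mmol/L and nothing else in the documents corrects it. That the literal flag would be nearly empty rests on the assumed lactate distribution.

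With the unit read as mmol/L, the flag is a post-arrival variable that the intervention can change, which contradicts the SAP's description of the weighting covariates as baseline. For baseline testing of 50% or more and 30% activation, the bias is at most about 0.8 to 2.5 minutes toward no effect, against the 16-minute planning difference. It should be smaller after adjustment for the other severity measures, and it is zero if everyone was already tested. The baseline testing rate, the share truly high and the 15 to 45 minutes are not in the documents.

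The scope is sepsis-cohort analyses, and only if the parallel-trends pre-test fails. The main adjusted model is not affected.

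**What to change.** In the SAP, Data analysis:

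1. Confirm the unit against the dataset and state the threshold in mmol/L.
2. Remove the lactate flag from the fallback weights. If it is kept, give a time window for the test and report the weighted analysis with and without it.

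A separate not-tested level, as used for SARS-CoV-2, would stop the pooling of untested with tested-low patients. It is not sufficient alone, because the weights would still balance testing, which the intervention can change.

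The cost is a line or two of SAP text and, if the flag is kept, one extra model run. Removing it loses one severity marker from the weights, while SOFA, acute physiology score and first vital signs remain.

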#### Primary and secondary outcome analysis covariates

Variables listed below will be included in multivariable adjusted analyses for primary and secondary outcomes listed above. Variables are also included in any associated subgroup and sensitivity analyses for these outcomes. For heterogeneity of treatment effect analyses, where continuous variables are categorized or dichotomized, the corresponding adjustment variable will also be categorized analogously in the adjustment model and for creation of the interaction term.

- Age (age, continuous)
- Female sex (sex, binary)
- Presentation from a long-term care facility (snf, binary)
- Weighted Elixhauser comorbidity score (elixhauser\_vw, continuous)
- Arrival to ED via ambulance (arrival\_mode, binary)
- English is preferred language (english\_preferred\_yn, binary)
- First-available temperature in ED (vs\_temp\_cat, categorical, reference group = 1 [temp 36-38°C])
- First-available systolic blood pressure in ED (**vs\_sbp**, continuous)
- Acute physiology score (aps\_24h, continuous)
- ED SOFA score (**sofa\_ed**, continuous)

• ED-diagnosed infection source (**source\_ed\_final\_simpler**, categorical, reference group = 1 [pneumonia])

**Figure 2.** Adjustment variables for primary & secondary multivariable analyses. The primary exposure is intervention ED arrival post-intervention and the primary outcome is door-to-antibiotic time. White symbols indicate potential confounders or precision variables included in the multivariable model, gray symbols represent an unobserved variable, and blue symbols (other than the outcome) represent an ancestor of outcome not included in the multivariable model.

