## 3. TRIAL DESCRIPTION

#### 3.1 Background

Sepsis, the combination of infection and acute organ dysfunction, is a common, morbid, and often lethal syndrome. Sepsis hospitalizes 1.3 million patients each year, kills 20%, and costs \$23.7 billion. Early, appropriate antibiotic initiation is critical: sepsis survival decreases with every hour's delay.  While guidelines and government mandates thus emphasize prompt antibiotics, international guidelines' have admitted a lack of data to support the feasibility or implementation of their one-hour door-to-antibiotic goal.

Among patients presenting to the emergency department (ED) with sepsis, we previously found that non-patient contextual cues could improve rapid antibiotic initiation, whereas ED busyness was associated with delayed antibiotics. I also discovered five-fold variation between physicians in median door-to-antibiotic time. ED care reorganization could bypass these cognitive, stylistic, and resource barriers to timely sepsis treatment. In fact, ED protocols linking prehospital notification to a multidisciplinary, team-based response are common and effective for trauma, stroke, and myocardial infarction, conditions that are less common and less mortal than sepsis but require similarly time-sensitive treatment. Given that sepsis has a less definitive presentation, however, analogous protocols for sepsis could waste resources or promote anchoring bias and overtreatment of patients without sepsis, issues observed with door-to-antibiotic standards for pneumonia.

We hypothesize that reorganizing ED sepsis care around multidisciplinary "Code Sepsis" teams activated prior to or upon patients' ED arrival will reduce door-to-antibiotic times — with tolerable overtreatment rates — by mobilizing personnel, systematizing illness severity and infection risk assessment, facilitating test completion, and eliminating any gap between treatment decision and antibiotic infusion. This study will therefore evaluate the effectiveness and tradeoffs of a Code Sepsis program for ED sepsis patients.

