#### 6.5 Variables/data elements

- Patient medical record number(s)
- Patient encounter ID code
- Hospital/facility
- Date of birth
- Age
- Sex
- Race

- Ethnicity
- Marital status
- Preferred language
- Insurance status/type
- Address/zip code (for determination of residence at a nursing facility or other long-term care facility and estimation of socioeconomic status)
- Social Security Number (to assist matching of encounter data to Social Security Death Index and Utah state death records)
- ED disposition
- Hospital disposition
- Date/time of all events related to ED visit and hospitalization (e.g. ED arrival & departure, hospital admission & discharge)
- Date/time antibiotics administered
- Antibiotic utilization
- APACHE II score
- APACHE IV score
- Acute physiology score
- Charlson index
- Elixhauser index
- SOFA score
- Baseline SOFA score over preceding 10 years
- Source of admission (e.g. home, SNF, LTAC, outside hospital)
- Source of infection
- Clinician infection determination, patient illness severity, sepsis status, and agreement with Code Sepsis activation
- Sepsis presence/absence
- Culture results
- Admission diagnosis
- Mode of arrival to ED
- ED triage data including triage acuity score
- Resident involvement in ED care
- Results of all laboratory testing
- Date/time of all laboratory testing
- ED length of stay
- ED vital signs
- ED medications
- ED interventions/procedures
- Date/time, elapsed time, and type of ED events including provider interaction, room placement, disposition
- Date/time of diagnostic testing, vasopressor initiation and other interventions, and management
- Date/time of interventions
- Date/time of blood or body fluid cultures
- Discharge diagnosis and procedure codes
- Billing diagnosis and procedure codes
- Diagnosis-related group
- Hospital length of stay

Code Sepsis I protocol Version 3.0

- In-hospital mortality
- Long-term mortality (e.g. 30d, 90d and 1y mortality)
- Healthcare charges
- ED patient census
- Number of ED beds
- ED patient flow (including counts of patient arrivals, boarding, and admissions)
- Attending physician ED staffing
- Nurse staffing
- Trauma registration status
- Allergies
- Adverse drug reaction events and date/time
- Code Sepsis team activation (Y/N)
- Code Sepsis activation date/time
- Code Sepsis care process completion date/times
- Code Sepsis team function
- Code Sepsis team composition (by role)
- Code Sepsis process adherence

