### Data analysis

Analyses for causal inference regarding primary, secondary and safety outcomes will employ a quasi-experimental method called *difference-in-difference* (DID) analysis to control for secular trends and confounding of unknown individual factors associated with the outcome of interest. The DID approach will provide an estimate of the effect of the Code Sepsis intervention on primary, secondary, and safety outcomes by comparing the intervention and control hospitals during the pre- and post-implementation periods (Figure 1).

For the primary outcome, DID analysis will use multivariable linear regression to compare the adjusted mean door-to-

antibiotic time (primary outcome) at the intervention hospital

pre- versus post-implementation of the Code Sepsis protocol using the measured change at contemporaneous control non-intervention hospitals to control for pre-/post-intervention changes not attributable to protocol implementation after adjustment for potential confounders.

The following equation will be used to estimate the adjusted mean differential change in the primary outcome, door to antibiotic time:

$$Y_{igt} = \beta_0 + \beta_1 Int_g + \beta_2 Post_t + \beta_3 (Int_g * Post_t) + \beta_4 Cov$$

Where  $Y_{igt}$  is the door-to-antibiotic time for patient *i* treated at an intervention or non-intervention ED *g* at pre- or post-intervention time *t*. *Int* is a binary indicator for the subject being treated at an intervention hospital; *Post* is a binary indicator the post-intervention period; and *Cov* represents a vector of patient-level covariates. The  $\beta_3$  parameter from the regression model presented above estimates the adjusted mean differential change in door-to-antibiotic time observed in the Code Sepsis intervention hospital compared to the control hospital. We will consider the Code Sepsis intervention to have had an impact if  $\beta_3$  is statistically significant and different from zero.

The parallel trend assumption will be tested using the approach outlined by Callaway and Sant'Anna. This approach allows for testing the parallel trend assumption after conditioning on covariates. This approach is

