#### Heterogeneity of treatment effect for primary outcome

Potential heterogeneity of treatment effect (HTE) will be evaluated using a differences-in-differences-indifferences approach adding interaction terms for subgroups versus study phase and versus control/intervention ED, and a three-way interaction between subgroup, study phase, and control/intervention ED. Subgroup results will be considered descriptive and will be referenced to the overall treatment effect from the primary analysis. The subgroup analyses are not confirmatory, hence no corrections for multiple comparisons will be made.

The following are predefined subgroups for HTE analyses:

- Age (<65 years vs ≥65 years)
- Sex (male vs female)
- Presence of hypotension on ED arrival (SBP <90 or MAP <65)
- Arrival to hospital via ambulance
- Source of infection
- APS quartiles

We will use the following DID formula for HTE analyses:

$$Y_{igts} = \beta_0 + \beta_1 Int_g + \beta_2 Post_t + \beta_3 Sub_s + \beta_4 (Int_g * Post_t) + \beta_5 (Post_t * Sub_s) + \beta_6 (Post_t * Int_g * Sub_s) + \beta_7 Cov$$

Where  $Y_{igts}$  is the door-to-antibiotic time for patient *i* treated at an intervention of non-intervention ED *g* at pre- or post-intervention time *t* from the cohort subgroup *s*. *Int* is a binary indicator for the subject being treated at an intervention hospital; *Post* is a binary indicator the post-intervention period; *Sub* is a binary indicator (or group indicator in the case of APS quartiles) of the subgroup; and *Cov* represents a vector of hospital- and patient-level covariates. The  $\beta_6$  parameter from the regression model presented above estimates the effect measure modification for door-to-antibiotic time in pre-specified subgroups. We will consider the Code Sepsis intervention to have had an impact on the subgroup if  $\beta_6$  is statistically significant and different from zero.

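### No measure of ED load enters any specified model, so a site-specific change in load between phases would enter the difference-in-differences estimate

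*SAP*

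**What the plan says.** The SAP's Data analysis section estimates the effect as β3, the intervention-site by post-period interaction. It describes the covariate term by saying that it "represents a vector of patient-level covariates". The section on primary and secondary outcome covariates then lists eleven variables, introduced by "Variables listed below will be included in multivariable adjusted analyses for primary and secondary outcomes listed above", and carries them into the associated subgroup and sensitivity analyses. They are age, sex, long-term care residence, comorbidity score, arrival by ambulance, preferred language, first temperature, first systolic pressure, acute physiology score, SOFA score and infection source.

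The protocol gives reasons to expect ED load to matter, and the means to measure it:

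- Section 3.1 reports the investigators' own finding that "ED busyness was associated with delayed antibiotics".
- Section 6.5 collects "ED patient census", the number of ED beds, physician and nurse staffing, and "ED patient flow (including counts of patient arrivals, boarding, and admissions".

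None of these load variables is in the covariate list, the safety covariate list, the propensity-score list or the code for either causal diagram. The heterogeneity equation says its covariate term "represents a vector of hospital- and patient-level covariates", but no hospital-level covariate is named anywhere. The propensity list does include "ED arrival at nightime (10 pm to 6:59 am), ED arrival on weekend", and those weights apply only if the parallel-trends pre-test fails.

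**The concern.** Difference-in-differences removes fixed differences between sites and changes shared by all sites. It does not remove a change that occurs at one site and not the others. There is a single treated ED, so anything that shifts there relative to the controls between the two analysis years is inseparable from the intervention unless it is measured and modelled.

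ED load is a natural candidate. The protocol itself ties it to the primary outcome. The EDs also differ in size: Protocol Table 1 gives 56, 28 and 35 ED beds for 89,000, 49,000 and 65,000 annual visits, so a shock common to the region need not move their load equally. The post-intervention year runs from February 2020 to February 2021, and the SAP already treats it as unusual by putting SARS-CoV-2 test status in the weights.

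At stake is the reading of β3. A relative fall in load at the intervention ED would look like faster care under Code Sepsis, and a relative rise would mask a real gain.

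**Working it through.** **1. Whether another part of the plan covers it**

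- *Parallel-trends pre-test.* The SAP acknowledges that it uses pre-implementation data only, so it cannot detect a load change that arises in the post phase.
- *Propensity weights.* They are used only if that test fails, and they contain no load variable.
- *Interrupted time series.* It allows site-specific trends through its time-by-site term, so a gradual divergence in load would be at least partly absorbed. A step that coincides with the post period still falls into the site-by-post term.
- *Causal diagram.* It shows several unadjusted causes of the outcome (heart rate, respiratory rate, white count, lactate, oxygen saturation) but not load, so the SAP records no reason for leaving load out.

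**2. Standard error of β3**

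Inputs from SAP, Power: 1,650 sepsis patients a year at the intervention ED, 2,200 at the control EDs together, SD 75 minutes, and 90% power for 16 minutes. SAP, Data analysis sets p < 0.05, taken here as two-sided. Patients are treated as independent and no covariate gain is counted.

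- Full annual counts in each one-year phase: SE = 75 × √(2/1,650 + 2/2,200) = 3.45 min. Power for 16 min = Φ(16/3.45 − 1.96) = 99.6%.
- This does not reproduce the stated 90%. The SE implied by that statement is 16/(1.96 + 1.28) = 4.94 min. Halving the counts per phase (825 and 1,100) gives SE 4.89 and power 90.6%, which is close. The simulation details are not in the documents. The stated figure is conservative on its own inputs, and the present point does not depend on it.

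Both SEs are carried forward.

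**3. Shift in β3 under assumed load effects**

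The documents give neither a slope nor a load change. The following is assumption:

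- Slope: 2 to 6 min of delay per 10-point rise in ED occupancy.
- Differential pre-to-post change, intervention minus control: 5 to 20 points.
- Shift = (slope/10) × differential change. Low end 0.2 × 5 = 1 min; high end 0.6 × 20 = 12 min.
- Shift that puts the expected estimate at p = 0.05: 1.96 × 3.45 = 6.8 min, or 1.96 × 4.94 = 9.7 min. At that point the chance of a significant result with no true effect is about one half.

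Chance of p < 0.05 with no true effect:

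| Shift (min) | SE 3.45 | SE 4.89 |
|---|---|---|
| 2.5 | 11% | 8% |
| 5 | 30% | 18% |
| 10 | 83% | 54% |

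**4. Check in a gamma model**

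The SAP says it will use gamma regression. A log-link gamma difference-in-differences was simulated 200 times per setting, with full annual counts, no true effect, and an assumed 15 min of delay per SD of load.

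| Differential load change | Without load term | With load term |
|---|---|---|
| 0 | −0.3 min, 2.5% rejected | −0.3 min, 4% rejected |
| −0.25 SD | −3.4 min, 16% | +0.3 min, 5.5% |
| −0.5 SD | −7.7 min, 60% | −0.2 min, 6% |

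Load is measured without error in this simulation, so the correction shown is a best case.

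**5. Night and weekend arrival**

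If the share of night or weekend arrivals changes differentially by 1 to 5 percentage points, and such arrivals wait 10 to 30 min longer (both assumed), the shift is 0.01 × 10 = 0.1 min to 0.05 × 30 = 1.5 min.

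**The case against.** The strongest reply is that the plan contradicts nothing. A reader might infer that the SAP breaks its own adjustment rule, since it promises to adjust for factors plausibly tied to both the outcome and the site or phase. The documents do not support that reading. The rule is confined to demographic and clinical parameters, in both the SAP and Protocol section 7.2, and the primary equation speaks of patient-level covariates. ED load is an operational measure, so its absence is a design choice and not a breach.

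A reader might also infer that β3 will be biased, or biased in favour of Code Sepsis. That does not follow either. No passage shows or predicts a differential change in load, and the direction is open. If load moved equally everywhere, the design already deals with it.

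The size is assumed throughout. If the two ranges in step 3 are treated as uniform, about 22% of combinations exceed 6.8 min and about 4% exceed 9.7 min. At the lowest slope the largest shift is 0.2 × 20 = 4 min, so neither threshold is reached. Precision is no argument for the change, because power on the planning inputs is already ample.

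Finally, some load measures could be consequences of the intervention. Protocol section 8.1.3 foresees resources drawn away from other patients, and section 3.7.2 lists room-placement and ED-departure timing as exploratory outcomes. Adjusting the primary model for census or boarding could remove part of the effect or introduce bias.

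All of this stands, and it limits the strength of the point and the form of the remedy. It does not answer why a collected factor that the protocol links to the primary outcome is neither modelled nor discussed.

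**Conclusion.** The omission is real and worth correcting, as a conditional weakness and not a demonstrated bias. A differential change in ED load would enter β3 in either direction, and no planned analysis would remove it if it came as a step at the post period. The 1 to 12 minute range and the simulated error rates rest on assumed slopes and load changes; the documents support only the mechanism. Night and weekend arrival are a side issue, at 0.1 to 1.5 minutes on assumed inputs. The case for acting is that the trial has one treated ED, the variable is already collected, and a version of it exists that is fixed before the patient's care begins.

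**What to change.** 1. Add to the SAP's primary and secondary covariate list one arrivals-based measure of ED load at patient arrival: arrivals in a stated number of preceding hours, divided by ED beds. It precedes the patient's own care, and Code Sepsis cannot change it. At a minimum, prespecify the primary difference-in-differences model with this term as a sensitivity analysis.
2. Use census or boarding only in a sensitivity analysis, reported beside the model without them. They capture crowding that arrival counts miss, but the intervention may affect them.
3. Tabulate load by site and phase, so readers can see whether a differential change occurred and in which direction.
4. Add load to the causal diagram, with a sentence on how it is handled.
5. Optionally, add night and weekend arrival, which are already defined for the weights.

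The cost is SAP wording and a derived variable; no new data collection is needed. An arrivals-based term controls load only partly, so item 3 should be kept even if item 1 is adopted.
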